weight loss at the end of the reward period. We used a two-sided alpha of 0.025 to account for the multiple comparisons between treatment groups (including for hypotheses 1b and 1c, which compare only two groups). We chose a clinically meaningful minimal detectable difference of 11 lbs. (5 kg). This was the weight loss experienced by the lifestyle management arm of the Diabetes Prevention Program randomized trial, which experienced lower rates of the incidence of diabetes. According to data from the 2012 NHANES, 11 lbs. is 5% of the average weight of 233 lbs. for obese men, and the FDA defines a weight loss drug as clinically effective if mean weight loss in the drug group is at least 5% of baseline weight. With these assumptions we would require full data on 21 patients per treatment arm at follow-up, or 28 assuming 20% loss to follow-up, in order to have 80% power to reject hypothesis 1a. In order to conduct subgroup analyses with reasonable precision, and to increase the power to detect differences in weight regain between reward groups (hypothesis 1c), we will increase enrollment to 80 patients in the no-reward arm, and we will increase the ratio of patients randomized to control versus either reward group from 1:1 to 1:1.25 for a total of 280 patients (80 usual care+100 in each reward arm). This provides a minimum detectable difference of 5.1 lbs. between treatment arms, and 4.5 lbs. if the reward arms are combined. In the three studies in Table 1, the average weight loss in the control groups at the end of follow-up was 1.6 lbs. Thus, we expect 80% power to detect weight loss as small as 6.7 lbs. in each reward group. At the end of the reward period, the average weight losses in the reward groups was 10 lbs. (range, 14 to 3.7) among the trials in Table 1. In the JAMA (2008) study, 50% of the reward group achieved their goal of 16 lbs. weight loss in 16 weeks. Thus, we have the power to detect achievable and clinically important weight losses across treatment arms.

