With 100 patients per reward arm, the minimum detectable difference for hypotheses 1b and 1c is 4.8 lbs. We will have power of 0.94 for the one-sided test of hypothesis 1b (non-financial rewards are not inferior to financial rewards). The power for hypothesis 1c (regain is lower in the non-financial compared to financial reward arm) depends on expectations of regain. We extrapolated weight regain from the trials in Table 1 in two ways: a) by assuming the weekly weight regain between the end of rewards and the last measurement continued; and b) by using data from a systematic review that found that in randomized trials of lifestyle changes for weight loss with a one year follow-up, the mean weight loss at one year was about half the weight loss achieved at 6 months. (See 2.0 Introduction for details.) We estimate that the weight regain by 12 months in the financial reward arms would be around 7.2 lbs. Thus, in order to have 80% power to reject hypothesis 1c, regain in the non-financial reward arm would need to be at most 2.4 lbs. (i.e.,  $7.2-4.8=2.4$  lbs.). The power for subgroup analyses will be limited. Simulations suggest our study sample would need to increase four fold to detect an interaction between female and treatment arm with the same power as the main analysis. We will interpret the subgroup results as exploratory, although we note that the proposed study will enroll 5 times as many female Veterans (n=70) as were enrolled in the JAMA (2008) (n=3) and JGIM (2011) (n=11) trials, combined, and more than the total enrollment of either of those trials.

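### The stated detectable differences (5.1, 4.5 and 4.8 lb) assume no loss to follow-up although section 5.6.a assumes 20%; Table 1 gives different values, and the 0.94 power for hypothesis 1b has no clear alpha

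*Combined protocol and SAP*

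**What the plan says.** The sample-size text in section 5.6.a assumes an SD of 11.0 lb for weight loss, 80% power and a two-sided alpha of 0.025, which it extends to the other hypotheses ("including for hypotheses 1b and 1c, which compare only two groups"). For an 11 lb difference it asks for full data on 21 patients per arm, "or 28 assuming 20% loss to follow-up, in order to have 80% power to reject hypothesis 1a". It then raises enrolment to 80 usual care and 100 per reward arm, partly "to increase the power to detect differences in weight regain between reward groups (hypothesis 1c".

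For that enlarged trial it states:

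- "This provides a minimum detectable difference of 5.1 lbs. between treatment arms, and 4.5 lbs. if the reward arms are combined"
- "Thus, we expect 80% power to detect weight loss as small as 6.7 lbs. in each reward group" (1.6 lb in controls plus 5.1 lb)
- "With 100 patients per reward arm, the minimum detectable difference for hypotheses 1b and 1c is 4.8 lbs"
- for hypothesis 1c, "regain in the non-financial reward arm would need to be at most 2.4 lbs" (7.2 minus 4.8)
- "We will have power of 0.94 for the one-sided test of hypothesis 1b"

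Table 1 in section 2.0 has entries for the proposed study that are labelled as minimum detectable differences. At the end of rewards they are -1.6 for usual care and -8.1 for each reward arm. At follow-up they are -3.1 for the lottery and -8.1 for the raffle.

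Sections 5.1.c and 5.2.a give 280 as the enrolment target. Section 5.1.c also allows up to 350 to be consented and reports that enrolment stopped, at least for the time being, at 274.

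**The concern.** The plan separates patients enrolled from patients with data when it derives the minimum size, but not when it states what the final size can detect. A reader will take 5.1, 4.5 and 4.8 lb as allowing for the 20% loss mentioned just before them. If they do not, the trial's sensitivity is overstated, most importantly for hypothesis 1c, which tests the idea about regain that motivates the study and is a stated reason for the larger sample.

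Two further inconsistencies affect the same figures. Table 1 gives different numbers under the same label. And hypothesis 1b is covered by a two-sided 0.025 in one paragraph and called a one-sided test in the next, with no alpha attached to the 0.94. Null results for 1a and 1c, and any conclusion on 1b, will be read against these numbers.

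**Working it through.** **Inputs (section 5.6.a).** SD 11 lb; two-sided alpha 0.025 (z = 2.2414); 80% power (z = 0.8416); enrolment 80/100/100; loss 20%; margin for 1b 2.5 kg = 5.51 lb; control loss 1.6 lb; expected 12-month regain in the financial arm 7.2 lb.

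**Formula.** MDD = (2.2414 + 0.8416) × 11 × √(1/n1 + 1/n2) = 33.91 × √(1/n1 + 1/n2).

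**Reproducing the plan, complete data.**

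- 80 v 100: 33.91 × 0.1500 = 5.09 lb (stated 5.1)
- 80 v 200: 33.91 × 0.1323 = 4.49 lb (stated 4.5)
- 100 v 100: 33.91 × 0.1414 = 4.80 lb (stated 4.8)

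All three match with every enrolled patient contributing.

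**Applying the plan's 20% loss (64/80/80).**

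- 64 v 80: 33.91 × 0.1677 = 5.69 lb
- 64 v 160: 33.91 × 0.1479 = 5.02 lb
- 80 v 80: 33.91 × 0.1581 = 5.36 lb

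Power at a stated difference d is Φ(d/SE − 2.2414). For 5.1 lb, SE = 11 × 0.1677 = 1.845, so power = Φ(2.765 − 2.241) = 0.70. For 4.5 and 4.8 lb it is 0.700 and 0.698.

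Derived claims: 1.6 + 5.69 = 7.3 lb (stated 6.7), and 7.2 − 5.36 = 1.8 lb (stated 2.4).

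**Sensitivity.** The documents give no R² for the covariate, so the R² values below are assumptions. So are the 30% loss and the split of 274 in the planned ratio. With adjustment, the SD is multiplied by √(1 − R²).

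| Scenario | Each reward arm v control | Combined v control | Between reward arms | Power at stated differences |
|---|---|---|---|---|
| Complete, unadjusted | 5.09 | 4.49 | 4.80 | 0.80 |
| 20% loss, unadjusted | 5.69 | 5.02 | 5.36 | 0.70 |
| 20% loss, R² 0.10 | 5.40 | 4.76 | 5.09 | 0.75 |
| 20% loss, R² 0.20 | 5.09 | 4.49 | 4.80 | 0.80 |
| 30% loss, unadjusted | 6.08 | 5.36 | 5.73 | 0.63 |
| 274 enrolled, 20% loss, unadjusted | 5.75 | 5.07 | 5.42 | 0.69 |

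**Table 1.** Reward arm versus usual care: 8.1 − 1.6 = 6.5 lb, against 5.1 lb in 5.6.a. At 80 v 100 complete, SE = 1.65, so 6.5 lb has power Φ(3.939 − 2.241) = 0.955. It is therefore not the 80% detectable difference. Raffle versus lottery: 8.1 − 3.1 = 5.0 lb, against 4.8 lb.

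**Hypothesis 1b, margin condition, true difference 0.** Power = Φ(5.51/SE − z), where SE = 11 × √(2/n).

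| One-sided alpha | 100 per arm | 80 per arm |
|---|---|---|
| 0.05 | 0.971 | 0.936 |
| 0.025 | 0.943 | 0.887 |
| 0.0125 (one tail of two-sided 0.025) | 0.903 | 0.823 |

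The 0.94 matches one-sided 0.025 with complete data. It would also match one-sided 0.05 after 20% loss. The rule for 1b also requires the non-financial arm to beat usual care, and none of these powers includes that.

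**The case against.** **Correct arithmetic, disclosed basis.** The figures are right for complete data, and the 4.8 lb statement names its 100 patients per arm. That stands. The fault is that the 20% loss was not carried forward.

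**Planned mitigation.** The analysis adjusts for baseline weight (for 1c, week-16 weight change), imputes missing weights from medical records and seeks a final weight from patients who withdraw. The 0.70 credits none of this, so it is a scenario and not a bound. But the power text claims nothing from these sources, and 5.6.a expects only a small efficiency gain from the repeated-measures model. Adjustment alone would need an R² of about 0.20 to restore the stated figures.

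**The consent ceiling.** 350 × 0.80 = 280, so 350 could have been meant as the allowance. No section says so, and sections 5.1.c, 5.2.a and 5.6.a all treat 280 as enrolment. The pause at 274 came with the coronavirus outbreak and is no evidence about the original design.

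**Other points that stand in part.** The SD is stated for weight loss and is carried over to regain. The plan does this itself, so both 2.4 and 1.8 lb inherit that uncertainty. The 0.05 route to 0.94 is possible but conflicts with the plan's 0.025. The second Table 1 gap is only 0.2 lb. The whole shift is small against 11 lb, which limits the seriousness but does not make the stated figures right.

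**Conclusion.** The concern holds. On the plan's own inputs, 5.1, 4.5 and 4.8 lb are complete-data figures. At its own 20% loss they are 5.7, 5.0 and 5.4 lb, and power at the stated differences is about 0.70 instead of 0.80. This assumes SD 11 lb for every comparison, no covariate adjustment and nothing recovered by imputation. Table 1 disagrees with 5.6.a, clearly for usual care (6.5 against 5.1 lb) and slightly between reward arms (5.0 against 4.8 lb).

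For 1b, 0.94 is not shown to be wrong, but its level is ambiguous, it makes no visible allowance for loss, and it covers only the margin. Depending on the level (one-sided 0.025 or 0.0125), power for that condition is 0.94 or 0.90 with complete data, and 0.89 or 0.82 after 20% loss.

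The practical effect falls on 1b and 1c. Hypothesis 1a at 11 lb is not threatened: even at 64 v 80, power is Φ(11/1.845 − 2.241), above 0.99.

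**What to change.** Replace the power statement in section 5.6.a with text along these lines:

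> Assuming SD 11 lb, two-sided alpha 0.025, 80% power, no covariate adjustment and no information recovered by imputation, the minimum detectable differences are 5.1 lb (each reward arm versus usual care), 4.5 lb (reward arms combined versus usual care) and 4.8 lb (between reward arms) with complete data on 80/100/100, and 5.7, 5.0 and 5.4 lb with 20% loss (64/80/80). The detectable reward-arm loss is 6.7 or 7.3 lb and the hypothesis 1c regain limit 2.4 or 1.8 lb, respectively.

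- If the sponsor wants to rely on adjustment or imputation, state the R² or the share of information assumed to be recovered.
- For 1b, state the one-sided alpha actually used and give the matching power (0.025: 0.94 complete, 0.89 at 20% loss; 0.0125: 0.90 and 0.82). Say that it covers the margin condition only. The choice of level is the sponsor's.
- In Table 1, with usual care at -1.6, change the end-of-reward value in the reward arms to -6.7 (complete data) or -7.3 (20% loss), and make the lottery-raffle gap at follow-up 4.8 or 5.4 lb. If -8.1 and -3.1 are expected values, relabel them instead.

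The cost is a text and table correction and slightly less favourable figures. No extra patients are needed, and no analysis or decision rule changes.

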**Table 1. Three model studies of financial rewards for weight loss, and the proposed study**

Study characteristics	JAMA (2008) 	JGIM (2011) 	Annals (2013) 	Proposed study
Setting	Philadelphia VAMC (95% male)	Philadelphia VAMC (83% male)	Employees of Children's Hospital (89% female)	Seattle VAMC
Weight loss goal	1 lb./week	1 lb./week	1 lb./week	1 lb./week
Trial arms (participants per arm)	Usual care (n=19) Lottery: expected value ~\$90/month; (n=19) Deposit contract: max \$75/month (n=19)	Usual care (n=22) Deposit contract: max \$84/month (n=44)	Usual care (n=35) Individual: \$100/month (n=35) Group: \$500/month split among 5 patients (n=35)	Usual care (n=80) Financial lottery (n=100): expected value \$100/month; Non-financial raffle (n=100): expected value ~\$100/month.
Duration of rewards/total follow-up	16 weeks/28 weeks	32 weeks/68 weeks	24 weeks/36 weeks	16 weeks/32 weeks
Weight change at termination of rewards (lbs.)	Usual care: -2.9 Lottery: -13.1* Deposit contract: - 14.0*	Usual care: -1.2 Deposit contract: - 8.6*	Usual care: -1.1 Individual: -3.7 Group: -10.6*	Min detectable difference Usual care: -1.6 Lottery: -8.1 Raffle : -8.1
Weight change at follow-up (lbs.)	Usual care: -4.4 Lottery: -9.2 Deposit contract: - 6.2	Usual care: -0.3 Deposit contract: - 1.2	Usual care: -0.9 Individual: -1.8 Group: -7.5*	Min detectable difference Lottery: -3.1 Raffle : -8.1

Our target population for this study is overweight or obese Veterans, ages 18-69. Please see section 5.4 for additional information on our inclusion/exclusion criteria.

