### 5.6.a. Data Analysis

All data will be analyzed at VA Puget Sound Health Care System by one of the data analysts and/or investigators.

We will use an intent to treat analysis. To test each hypothesis we will estimate an equation of the form

$\Delta Y_{it} = \beta_0 + \beta_1 Weight_{i0} + \beta_2 M_i + \beta_3 F_i + u_i$  (1) where  $\Delta Y_i$  is change in weight from baseline to follow-up time t

for patient i;  $Weight_{i0}$  is baseline weight for patient i; F is the financial rewards (arm 2); M is an indicator for assignment to non-financial rewards (arm 3); and u is a random error. To gain a small amount of efficiency we can also estimate (1) using repeated measures of change in weight from baseline to the three follow-up measures (16 weeks, 32 weeks and 12 months) using GEE models of the same form as equation (1), except with dummy variables for follow-up periods and interactions between these variables and the treatment group dummies.

Hypothesis 1a implies a test of superiority and will be assessed using two-sided tests of  $\beta_2 = 0$  for non-financial rewards, and  $\beta_3 = 0$  for financial rewards. Large positive or negative values of  $\beta_2$  and  $\beta_3$  are evidence against the null hypothesis of no difference between reward and non-reward groups.

Hypothesis 1b implies a non-inferiority test. We will reject the hypothesis that non-financial rewards are inferior to financial rewards if  $\beta_2$  is statistically significantly greater than zero (i.e., there was statistically significantly more weight loss in the non-financial reward arm than in usual care) and if  $(\beta_3 - \beta_2) < 2.5 kg$ , where  $(\beta_3 - \beta_2)$  is the adjusted difference in mean weight loss between the financial and non-financial reward arms, and 2.5 kg is half the 5 kg weight loss assumed to be clinically significant. Although there are no defined rules for choosing a range of indifference for a non-inferiority test, researchers often use half the minimum clinically significant amount. Values of  $(\beta_3 - \beta_2)$  that are statistically significantly larger than 2.5 kg are evidence against the hypothesis that non-financial rewards are not inferior to financial rewards.

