Hypothesis 1c implies a test of superiority and will be assessed using two-sided tests of  $(\beta_3 = \beta_2)$  in comparisons of weight change from week 16 to week 32 and 12 months, respectively. We will use weight change at week 16 in place of weight at baseline in equation 1, such that differences in weight regain between treatment arms will be adjusted for weight lost over weeks 1-16.

Because all secondary outcomes are continuous variables, a similar equation will be used to assess changes in secondary outcomes. These analyses explore how rewards affect constructs that are believed to mediate the effect of rewards on weight loss.

Missing weight measures will be imputed using data from patients' medical records for routine medical visits and methods developed and tested via simulation by [name] et al. These methods involve estimating longitudinal mixed-effects linear models of weight collected both through the trial and at routine clinic visits as a function of polynomials of time since enrollment, with random components for patient intercept and time, and using the predicted values from this model for any post intervention day as an estimate of what the patient's weight would have been on that day if he/she kept their follow-up appointment.

We assumed a standard deviation of 11.0 lbs. for weight loss based on the results of the JAMA (2008) and JGIM (2011) trials that were conducted in the VA and demonstrated statistically significant differences in

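### The 0.94 power stated for hypothesis 1b covers only the margin comparison; the power of the two-part rule depends on an effect over usual care that the plan does not state there

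*Combined protocol and SAP*

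**What the plan says.** Section 5.6.a (Data Analysis) defines the test of hypothesis 1b, which concerns weight loss at week 16, by two conditions joined by 'and'. The first is that β2 is significantly above zero, which the plan explains as meaning that "there was statistically significantly more weight loss in the non-financial reward arm than in usual care". The second is that the adjusted financial minus non-financial difference, β3 − β2, is below 2.5 kg, where "2.5 kg is half the 5 kg weight loss assumed to be clinically significant".

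The power statement comes later in the same section, after a sentence based on 100 patients per reward arm: "We will have power of 0.94 for the one-sided test of hypothesis 1b". It mentions neither usual care nor an assumed advantage over usual care.

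The other inputs are also in section 5.6.a: "We assumed a standard deviation of 11.0 lbs. for weight loss"; "We used a two-sided alpha of 0.025 to account for the multiple comparisons between treatment groups", which the plan extends to hypotheses 1b and 1c; and arm sizes of "80 usual care+100 in each reward arm". The section gives 5.1 lb as the minimum detectable difference between treatment arms. In section 2.0, the Table 1 entry for the proposed study at the end of rewards reads "Min detectable difference Usual care: -1.6 Lottery: -8.1 Raffle : -8.1".

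**The concern.** A rule that needs two successes cannot have more power than its weaker part. The plan says it has 80% power to detect 5.1 lb between a reward arm and usual care. If that were the true effect, the first condition alone would hold the power for hypothesis 1b to about 0.80, whatever the margin test does. A figure of 0.94 that is silent about the usual-care condition cannot describe the rule at that effect.

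The stake is how the 0.94 is read. It suggests a 6% risk of failing to confirm hypothesis 1b when the two rewards are equally effective. The rule can also fail by a second route: the reward arms perform alike, but the non-financial arm does not separate significantly from the 80 usual-care patients. The stated figure does not show that route. For hypothesis 1c, by contrast, the same paragraph says openly that power depends on an assumption (the expected regain).

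**Working it through.** I treat the coefficients as weight loss, as the plan's explanation of the rule does.

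**Inputs.** SD 11 lb; 80 usual care, 100 in each reward arm; margin 2.5 kg = 5.51 lb; two-sided 0.025 for comparisons with usual care (critical value 2.241). All are from section 5.6.a. I take the true difference between the reward arms as zero, which agrees with the equal lottery and raffle values in Table 1.

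**Step 1: reproduce 0.94.** SE(β3 − β2) = 11 × √(1/100 + 1/100) = 1.556 lb. At one-sided 0.025, power = Φ(5.51/1.556 − 1.960) = Φ(1.58) = 0.943. With a 5.5 lb margin it is 0.942. The usual-care arm does not enter. One-sided 0.0125 gives 0.90 and one-sided 0.05 gives 0.97, so one-sided 0.025 with no loss to follow-up is the reading that returns the plan's figure.

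**Step 2: the usual-care condition.** SE(β2) = 11 × √(1/80 + 1/100) = 1.650 lb. Power = Φ(d/1.650 − 2.241), where d is the true advantage over usual care. Three values of d can be drawn from the plan:

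- 5.1 lb, the minimum detectable difference at the planned sample size (section 5.6.a);
- 6.5 lb = 8.1 − 1.6, implied by the Table 1 cell at the end of rewards;
- 8.4 lb = 10 − 1.6, the average reward-arm loss in the earlier trials minus the average control loss (section 5.6.a).

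**Step 3: both conditions together.** The two tests share the non-financial arm. The correlation between β2 and −(β3 − β2) is (121/100)/(1.650 × 1.556) = 0.471. Joint power is the bivariate normal probability that both conditions are met.

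| d over usual care | Usual-care condition alone | Margin alone (one-sided 0.025) | Both | Both, margin at one-sided 0.0125 |
|---|---|---|---|---|
| 5.1 lb | 0.802 | 0.943 | 0.776 | 0.753 |
| 6.5 lb | 0.955 | 0.943 | 0.910 | 0.875 |
| 8.4 lb | 0.998 | 0.943 | 0.942 | 0.903 |
| 11 lb | >0.999 | 0.943 | 0.943 | 0.904 |

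A simulation with 2 million draws gave 0.776, 0.910, 0.942 and 0.943 for the 'Both' column.

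**Separate sensitivity: loss to follow-up.** The plan's phrase "or 28 assuming 20% loss to follow-up" belongs to its initial sample-size step, and no loss is applied to the 0.94. With complete cases of 64/80/80 (80% of each arm) and the margin at one-sided 0.025, the margin part alone has 0.887. The full rule has 0.66, 0.82 and 0.88 at 5.1, 6.5 and 8.4 lb.

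**The case against.** The strongest reply is that 0.94 is a correct number for what its sentence describes. The sentence follows one about 100 patients per reward arm and is glossed as non-financial not inferior to financial. Detectable differences against usual care are given separately. On this view a joint figure is missing but nothing is miscalculated. That stands: the fault is one of labelling and completeness, not of arithmetic.

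A second reply concerns the choice of effect. A reader might infer that the true power of the rule is simply below 0.94. The documents do not support that without a condition. At 8.4 lb, and at the 11 lb that the plan also calls a minimal detectable difference, joint power is 0.94 and the usual-care condition costs almost nothing. The 5.1 lb case is harsh by construction, since a minimum detectable difference is the effect with 80% power. The 6.5 lb comes from a cell labelled as a minimum detectable difference, and its 8.1 lb does not match the 6.7 lb that section 5.6.a derives from 5.1 + 1.6. It should not be presented as the planned effect.

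Third, the replacement figures depend on readings that the plan leaves open. If its two-sided 0.025 means one-sided 0.0125 for the margin test, they fall. If the margin condition is read literally, as a comparison of the estimate with 2.5 kg without a confidence limit, joint power at 6.5 lb would be about 0.955. But the margin part alone would then exceed 0.999, so that reading does not produce the plan's 0.94.

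Fourth, the figures with 20% loss mix in another matter. The plan intends to impute missing weights using medical-record data, so complete-case numbers are a reviewer's assumption and should not be used as the main correction.

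Finally, week-16 weight loss is a secondary outcome (section 3.0), and the 0.94 did not set the sample size. Both are true and limit the consequence. Neither makes the label right.

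**Conclusion.** The point holds in a conditional form. The 0.94 is the power of the margin comparison alone, while hypothesis 1b is decided by a two-part rule. The power of that rule depends on the advantage of non-financial rewards over usual care, which the power statement does not give. With complete data, SD 11 lb, equal reward arms, two-sided 0.025 against usual care and one-sided 0.025 for the margin, it is about 0.78 at 5.1 lb, 0.91 at 6.5 lb and 0.94 from 8.4 lb upward.

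The figure can therefore stand for the full rule only if one of the larger effects is assumed. It does not follow that the trial is underpowered for hypothesis 1b. The documents show only that the stated power is incomplete, and by how much under each effect they mention. That 0.94 omits the usual-care condition is certain from the text and the reproduction; the size of the shortfall is conditional on the effect and the alpha.

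**What to change.** In section 5.6.a, label 0.94 as the power of the margin component only. Add the joint power of the two-part rule, with the assumed effect over usual care and the alpha of each part. The sponsor first has to say which alpha applies to the margin test:

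- one-sided 0.025: 0.78, 0.91 and 0.94 at 5.1, 6.5 and 8.4 lb;
- one-sided 0.0125: 0.75, 0.88 and 0.90, with the margin component itself at 0.90 instead of 0.94.

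Figures that allow for loss to follow-up should be given separately, as a sensitivity range. The cost is one or two sentences, and a less favourable stated power unless a large effect over usual care is assumed. Sample size, conduct and the decision rule do not change.
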